4.4.3 Handling of Missing Values/Censoring/Discontinuations

Missing endpoints data will not be imputed, only subjects that completed the study are included on the mITT population.

4.5 Analysis of Secondary Objectives

4.5.1 Efficacy (Secondary)

Refer [Section 4.4.2](#) for the analysis of secondary objectives.

4.6 Exploratory Analysis

- **Analysis of number of ill days over 3 and 6 months:**

The number of ill days due to GI and respiratory illnesses over 3 months and 6 months separately on the ITT population who have completed the study for 3 months and 6

GlaxoSmithKline Consumer Healthcare Confidential

months will be summarized and analyzed using the same model as used in the primary analysis (Table 14.2.13.1.1 and Table 14.2.13.1.2).

- **Analysis of total number of ill days for GI and respiratory illness separately over 3, 6 and 9 months:**

Primary analysis and the above analysis will be repeated for total number of ill days for GI and respiratory illness separately at months 3, 6 and 9 based on the ITT population (Table 14.2.13.2.1 and Table 14.2.13.2.2 for GI illness) and (Table 14.2.13.3.1 and Table 14.2.13.3.2 for respiratory illness).

- **Analysis of total number of ill days due to GI and respiratory illnesses, school absenteeism (days), frequency (per month), severity by gender at 9 months:**

It will be summarized and analysed and presented as detailed for the primary and secondary endpoint respectively by gender (Table 14.2.13.4.1 and Table 14.2.13.4.2 for ill days due to GI and respiratory illnesses), (Table 14.2.13.7.1 and Table 14.2.13.7.2 for school absenteeism (days)), (Table 14.2.13.5.1 and Table 14.2.13.5.2 for frequency (month)) and severity of episodes (Table 14.2.13.6.1).

- **Analysis of change from baseline of HAZ, Height and Weight:**

Change from baseline in HAZ, height and weight will be summarised and analysed using the same ANCOVA model as mentioned for the BMI analysis (Table 14.2.13.8.1 and Table 14.2.13.8.2 for HAZ), (Table 14.2.13.9.1 and Table 14.2.13.9.2 for height), (Table 14.2.13.10.1 and Table 14.2.13.10.2 for weight).

- **Association between Gut integrity/health as measured by Lactulose: Mannitol test and Urinary Neopterin test with blood chemistry:**

Correlation between micronutrients (Vitamin A, B12, D (25 Hydroxy calciferol), E, folate, selenium, zinc, copper, and iron) and gut integrity/health as measured by Lactulose: Mannitol test and Urinary Neopterin test will be computed at baseline and at visit 10 (Table 14.2.13.11), Also, correlation between change from baseline micronutrients (Vitamin A, B12, D (25 Hydroxy calciferol), E, folate, selenium, zinc, copper, and iron) and change from baseline in gut integrity/health as measured by Lactulose: Mannitol test and Urinary Neopterin will be computed at month 9 (Table 14.2.13.12).

- **Summary of Number of Ill Days Due to GI Illness and respiratory illnesses and separately by School over Month 3, 6 and 9:**

Descriptive statistics tables for number of Ill days due to GI and Respiratory Illnesses by School (Table 14.2.14.1), number of Ill days due to GI Illnesses by School (Table 14.2.14.2) and number of Ill days due to Respiratory Illnesses by School (Table 14.2.14.3) will be presented.

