9.3.5 Other Analyses

As exploratory analysis, following analyses will also be performed:

- Analysis on number of ill days will be performed for those participants in ITT population who have completed the study for 3 months and 6 months separately.
- Analysis on number of ill days will be performed on GI and respiratory illnesses separately on those participants who are in ITT population and have completed the study for 3 months, 6 months and 9 months.
- Total number of ill days (GI and respiratory illnesses), number of episodes (GI and respiratory illnesses), and severity of GI and respiratory illnesses by gender will also be analysed.
- Total number of ill days (GI and respiratory illnesses), number of episodes (GI and respiratory illnesses), and severity of GI and respiratory illnesses by screening, end of study, and change from baseline in DDS, energy, protein, carbohydrate and fat will also be analysed.

 GlaxoSmithKline	Document Name	Clinical Study Protocol 204477		
	Type	Version	Document Identifier	Effective Date
	eldo_clinical_doc	5.0; Most-Recent; Effective; CURRENT	090032d580daa95e	10-Oct-2017 06:16:49
	Reason For Issue	Auto Issue		

The same model outlined above for primary outcome variable (Section 9.3.2) will be used for this secondary outcome.

Adjusted means, 95% confidence intervals, within treatment p-values for each treatment group, treatment group difference, 95% confidence interval of the difference and the between-treatment p-values based on the statistical model described above for each secondary outcome will also be presented.

All statistical tests of hypotheses will be two-sided and will employ a level of significance of $\alpha = 0.05$.

The assumptions of normality and homogeneity of variance will be investigated. Violation of these assumptions may be overcome using suitable transformation (for example, log) or performing appropriate non-parametric tests.

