4.4.1.2 Statistical Hypothesis, Model, and Method of Analysis

For the primary variable, primary analysis will be performed on participants on the mITT population.

The null hypothesis of interest is:

H0: There is no difference between the numbers of illness days for the product groups.

The alternative hypothesis of interest is:

H1: There is a difference in between the numbers of illness days for the product groups.

The number of ill days will be analysed using the analysis of variance (ANCOVA) model. The ANCOVA will have cluster (school) as a random effect, product group and gender as fixed effects and baseline IDDS as a covariate.

Adjusted means, 95% confidence intervals (CI), within product group p-values for each product group, product group difference, intracluster correlation, 95% confidence interval of the difference and the between-product group p-values based on the statistical model described above will also be presented ([Table 14.2.2.2](#)).

All statistical tests of hypotheses will be two-sided and will employ a level of significance of $\alpha = 0.05$.

The simulated data used for the sample size calculations were based upon the assumption of a Poisson distribution per product group. However, on observation of these simulated data, it was considered that these Poisson distributions were not heavily skewed and, as a result, normal distributions may be assumed. Consequently, a normality assumption has been adopted for both the generation of sample size and the intended approach to the statistical analysis.

However, the assumptions of normality and homogeneity of variance will be investigated and violation of these assumptions may be overcome using suitable transformation (for example, log or square root or Poisson regression using Proc Genmod) or by performing appropriate non-parametric tests (e.g., Van Elteren, rank ANCOVA).

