4.4.1.3 Supportive Analyses

As a part of sensitivity analysis a Mixed Model Repeated Measure (MMRM) model will be used. MMRM model will be just an analysis including multiple visits with defined structure of correlation among visits. In this study unstructured covariance matrix will be used. The number of ill days will be analysed using model with cluster (school) as a random effect; product group, gender, and visit and (product group and visit) interaction as fixed effects and baseline IDDS as a covariate.

This will be conducted on the primary efficacy endpoints on the ITT population ([Table 14.2.2.2a](#)).

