|---------|------------|----------------|----------------|----------------|
| | | (N = xxx) | (N = xxx) | (N = xxx) |
| | | Observed Value | Observed Value | Observed Value |
| MONTH 9 | n | xxx | xxx | |
| | MEAN | xx.xx | xx.xx | |
| | SD | xx.xxx | xx.xxx | |
| | SE | x.xx | x.xx | |
| | MEDIAN | x.xx | x.xx | |
| | MINIMUM | xx.x | xx.x | |
| | MAXIMUM | xx.x | xx.x | |

Test Group: Fortified malt based food + Dietary Counselling; Control Group: Dietary Counselling

Program: xxxxxx.sas

Source: Filename

Page x of y

Fortified malt based food

204477 Statistical Reporting and Analysis Plan Amendment 1 2 November 2018

Protocol 204477

Program Run Date: DDMMYYYY

14.2.13.4.2

Statistical Analysis of Number of Ill Days Due to GI and Respiratory Illnesses by Gender at Month 9

Modified Intent-to-Treat Population

Study Population: Modified Intent-to-Treat Population (N = xxx)

<By Variable >: XXXXXX (N = xxx)

| Visit | Group | N | Adjusted Mean | SE | 95% CI | P-Value | Intracluster Correlation | Comparison with Control Group | | |
|---------|---------------|-----|---------------|--------|--------------|---------|-----------------------------|-------------------------------|--------------|---------|
| | | | | | | | | Difference (SE) | 95% CI | P-Value |
| MONTH 9 | Test Group | xxx | xx.xx | xx.xxx | xx.xx, xx.xx | 0.xxxx | x.xxx | xx.xx (xx.xxx) | xx.xx, xx.xx | 0.xxxx |
| | Control Group | xxx | xx.xx | xx.xxx | xx.xx, xx.xx | 0.xxxx | | | | |

Test Group: Fortified malt based food + Dietary Counselling; Control Group: Dietary Counselling

Analysis was performed using ANCOVA model with cluster (school) as a random effect; product group and gender as fixed effects and baseline IDDS as covariate.

Difference is Test Group minus Control Group such that a negative difference favors the Test Group.

Intracluster correlation performed on complete model.

Confidence interval (CI) is presented as calculated (not truncated) and could present also negative values. Such negative values within CI no to be used for result interpretations.

Program: xxxxxx.sas

Source: Filename

Page x of y

Fortified malt based food

204477 Statistical Reporting and Analysis Plan Amendment 1 2 November 2018

Protocol: 204477

Program Run Date: DDDMMYYYY

Table 14.2.13.11

Correlation between Blood Chemistry and Gut Integrity Health by Lactulose: Mannitol and Urinary Neopterin Test by Time Point
Modified Intent-To-Treat Population

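### The exploratory by-gender analyses give each gender its own p-value, and nothing in the plan estimates or tests whether the product effect differs between boys and girls

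*SAP*

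**What the plan says.** SAP 4.6 covers four outcomes by gender at 9 months: ill days, school absenteeism, monthly frequency and severity. Its instruction is "It will be summarized and analysed and presented as detailed for the primary and secondary endpoint respectively by gender". The ill-days display, Table 14.2.13.4.2, is titled "Statistical Analysis of Number of Ill Days Due to GI and Respiratory Illnesses by Gender at Month 9". Its shell has a by-variable line with its own N, then adjusted means, a between-group difference, a 95% CI and a p-value. The footnote reads "Analysis was performed using ANCOVA model with cluster (school) as a random effect; product group and gender as fixed effects and baseline IDDS as covariate".

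The primary model in SAP 4.4.1.2 has the same terms: "The ANCOVA will have cluster (school) as a random effect, product group and gender as fixed effects and baseline IDDS as a covariate". The only interaction in the plan is in the repeated-measures sensitivity analysis of SAP 4.4.1.3, between product group and visit: "product group, gender, and visit and (product group and visit) interaction as fixed effects and baseline IDDS as a covariate".

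Protocol 9.3.5 asks for the same kind of analysis ("severity of GI and respiratory illnesses by gender will also be analysed"), calls it exploratory and names no interaction test. On testing, SAP 4.4.1.2 states "All statistical tests of hypotheses will be two-sided and will employ a level of significance of" 0.05, and Protocol 9.3.5 repeats that level for the exploratory analyses. Neither document says how the by-gender results are to be interpreted.

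**The concern.** A p-value within boys asks whether there is an effect in boys, and likewise for girls. Neither asks whether the two effects differ, and no other output does. When each half of the sample has only moderate power, a significant result in one gender and a non-significant result in the other is a common outcome even if the effect is identical. A report with two such p-values and no interaction estimate gives its reader nothing with which to correct that impression.

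There is also a specification error. Within a block run on one gender, a gender term cannot be estimated. The footnote matches the one under Table 14.2.2.2, the primary table, and appears to have been carried over. If the main-effects model were instead fitted once to everyone, it would impose the same product difference on both genders and separate blocks would have no purpose. On either reading the footnote and the layout do not fit together.

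**Working it through.** **Inputs.** Means 7.0 and 6.3, SDs 2.65 and 2.51, 215 per arm for 80% power, design effect (DE) 1.5, 323 completers per arm, 30% dropout, 924 randomised (Protocol 9.1, SAP 1.4). Gender split 50:50, limits 40% to 60% (SAP 3.2). Four schools, two per group (SAP 3.3). Two-sided alpha 0.05.

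**The plan's own figure.** Pooled SD = √((2.65² + 2.51²)/2) = 2.581. The normal approximation gives 214 per arm and the t-test gives 215 (power 80.1%). 215 × 1.5 = 322.5, so 323. 646/0.70 = 922.9, so 923, or 924 as 462 per arm. The sample size reproduces.

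**Power within one gender, identical effect of 0.7 days, 323/2 = 161.5 per arm.**

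- Full DE 1.5: effective n = 161.5/1.5 = 107.7. SE = 2.581 × √(2/107.7) = 0.352. Power = Φ(0.7/0.352 − 1.96) = 51%, against 80% overall. Treating the genders as independent, P(exactly one significant) = 2 × 0.512 × 0.488 = 50%; both 26%, neither 24%.
- Intracluster correlation (ICC) implied by DE 1.5 at 161.5 completers per school: 0.5/160.5 = 0.0031. With 80.75 of one gender per school, DE = 1 + 79.75 × 0.0031 = 1.25 and effective n is about 129, so power is 59%. Boys and girls share the school effects, so their estimates correlate: 0.0031/(0.0031 + 0.9969/80.75) = 0.20. P(both) = 37.6%, so P(exactly one) = 2 × (58.8% − 37.6%) = 42%.
- 40:60 split, full DE, independent genders: power 43% and 59%, P(exactly one) = 51%.

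In the first case, among trials with a significant overall result, exactly one gender is significant 57% of the time (simulation).

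**If product group is tested at school level.** School is a random effect with two schools per arm, and the SAP names no method for the degrees of freedom (df). A t-test on school means has 4 − 2 = 2 df. Simulating it within each gender, with shared school effects, gives:

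| ICC | Power per gender | P(exactly one significant) |
|---|---|---|
| 0.0031 | 25% | 36% |
| 0.01 (assumed) | 19% | 28% |
| 0.02 (assumed) | 15% | 21% |
| 0.05 (assumed) | 10% | 13% |

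The rate falls because power falls.

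**What an interaction test would do.** With equal effects and its assumptions met, it rejects 5% of the time. Its SE is √2 times the within-gender SE.

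- Full DE 1.5: √2 × 0.352 = 0.497. The 95% CI is ±0.97 days, and power for a 0.7-day difference between genders is Φ(0.7/0.497 − 1.96) = 29%.
- No DE, since a shared school effect cancels in this contrast: √2 × 2.581 × √(2/161.5) = 0.406. The 95% CI is ±0.80 days and power is 41%.

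A random school intercept alone ignores school-by-gender variation. If that component were 1% of the residual variance (assumption), the true variance of the contrast would be 1 + 80.75 × 0.01 = 1.81 times the modelled one, and the test would reject about 14% of the time under equal effects. At 2% the factor is 2.62 and the rejection rate about 23%.

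**The case against.** The strongest objection is that the plan commits no inferential error. A reader might infer that a gender-specific effect is to be declared by comparing the two p-values. The documents do not say so: the analyses are labelled exploratory, no interpretation rule is given, and Protocol 9.2.3 rests success on the overall ill-day comparison alone. Within-gender estimates with confidence intervals are also ordinary reporting in a trial that balances recruitment by gender. All of this stands. What remains is that the layout produces p-values by gender and no quantity that addresses a difference.

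A second objection concerns size. A reader might take a one-in-two chance of a split result as simply what the plan's assumptions imply. That figure applies the full design effect to half-size clusters and treats boys and girls in the same schools as independent. With shared school effects at the implied ICC it is 42%, and with school-level df it is lower still. The objection stands, so a range is given.

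Third, the remedy has limits. The interaction test has low power and can over-reject if the gender contrast varies between schools. This also stands. It favours reporting an estimate with its interval over relying on the test.

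**Conclusion.** The point holds as a minor one. The by-gender analyses answer two separate questions and leave out the comparison between genders. On the plan's inputs, with the target 50:50 split and the same 0.7-day effect in both genders, exactly one gender would reach p<0.05 in about 42% to 50% of trials. If product group is tested on about 2 school-level df the range is about 13% to 36%, over ICCs of 0.0031 to 0.05. Which range applies depends on a df method the SAP does not state, and the ICCs above 0.0031 are assumptions. Equal numbers per school are also assumed.

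The footnote is wrong for a table run by gender, but this is a labelling fault: the term would drop out and the product-group estimate would not change. The primary conclusion is untouched.

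**What to change.** - For ill days, frequency and absenteeism, replace the split runs with one model adding product group by gender. Report the interaction estimate with its 95% CI, and the within-gender differences with CIs from that model, without separate significance claims.
- Present by-gender severity (Table 14.2.13.6.1) descriptively, or with a matching interaction model. The chi-square or Fisher comparison repeated in each gender has the same gap.
- Correct the footnote of Table 14.2.13.4.2, and of the frequency and absenteeism tables if they copy it.
- State that the interaction test has low power and relies on little school-by-gender variation, and that a non-significant interaction is not proof of equal effects.

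The cost is one model term, revised shells and a sentence of interpretation. No new data are needed. The small downside is that the interaction CI will be wide, about ±0.8 to ±1.0 days against a planned effect of 0.7.

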1.4 Sample Size Calculation

The primary efficacy variable of the study is the total number of ill days due to GI and respiratory illnesses. The sample size has been calculated based on the assumption of an average of 7 ill days in the control group with a difference of 10% between the treatments.

Years Lost due to Disability (YLD) is a measure of the burden of disease from its morbidity. Below are data that are specific to India: As per the data from Global Burden Disease, WHO 2010 study (GBD, WHO, 2012; IHME, 2013) and Census India, 2011, YLD per child in the 5-9-year age group, due to diarrhea, LRTIs, other infectious disease and nutritional deficiencies is 8.274 days/child per year or 6.21 days/child per 9 months.

Thus, based on above data, approximately 7 ill days due to GI and respiratory illnesses per 9 months has been assumed in this proposed study population of 7-10 year olds.

The sample size is based on the primary endpoint. No sample size considerations have been taken into account for secondary objectives.

The simulated data were also used based upon the assumption of a Poisson distribution per study treatment. On observation of these simulated data, it was considered that these Poisson distributions were not heavily skewed and, as a result, normal distributions may be

assumed. Consequently, a normality assumption has been adopted for both the generation of sample size and the intended approach to the statistical analysis.

Because of assumption of Poisson distribution, estimates of variability were calculated as square root of mean.

Mean of control was assumed to be 7.0 and standard deviation (SD) was 2.65, mean of test group was 6.3 and SD was 2.51. To be able to achieve 80% power, 215 participants per treatment arm (Total = 430) will be required to complete the study in case of individual randomisation. This assumes 5% level of significance (two tailed t-test).

As this study is using cluster randomization, and design effect (DE) needs to be considered for sample size calculations. Scientific literature suggests, DE due to cluster sampling strategy can be assumed to be 1.5 [Rosner, B, 1986]. Same has been assumed in one study, which used three-stage systematic cluster sampling [Dandona R *et al*, 2008].

Using the following formula from Hemming *et al*, 2011:

$$N^* = N \times DE$$

Where N^* = Number of participants required for cluster randomized trial

N = Number of participants required for individual randomization

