3.3 Centers Pools

This study is conducted in multiple (4) schools, with two schools in each product group.

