| 
 9.3.2 9.3.3 | 
 For all ANCOVA analyses, "cluster (school)" will be included as a random | 
 Handling "cluster" as random effect would avoid over-parametrisation and would allow for intracluster correlation. |

| Protocol | Reporting & Analysis Plan | |
|---|--|---|
| Statistical Analysis section | Statistical Analysis Plan | Rationale for Changes |
| 
 9.3.5 | 
 effect instead of a fixed effect. Present the estimate of the intra cluster correlation in the ANCOVA tables. | 
 Adjusting for the intracluster correlation is necessary for a valid analysis. |

6 Template for Tables, Figures and Listings

This is a guideline which will give the guidance of product group labels that will be used for the table header and in the figures, listings and in the footnotes.

The product group labels for the column headings will be as follow:

Test Group and Control Group;

The product group comparison will be:

- Test Group vs Control Group

The order of the product groups will be following-

- 1st: Test Group
- 2nd: Control Group

In all the outputs following footnote will be added –

Test Group: Fortified malt based food + Dietary Counselling

Control Group: Dietary Counselling

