Study Population: Modified Intent-to-Treat Population (N=XXX)

Time point: Baseline

| | Test Group | | | Control Group | |
|-------------|--------------------|------------------------|-------------|--------------------|------------------------|
| | (N=xx) | | | (N=xx) | |
| | Lactulose Mannitol | Urinary Neopterin Test | | Lactulose Mannitol | Urinary Neopterin Test |
| Vitamin A | xx.x | xx.x | Vitamin A | xx.x | xx.x |
| Vitamin B12 | xx.x | xx.x | Vitamin B12 | xx.x | xx.x |
| Vitamin D | xx.x | xx.x | Vitamin D | xx.x | xx.x |
| Vitamin E | xx.x | xx.x | Vitamin E | xx.x | xx.x |
| Folate | xx.x | xx.x | Folate | xx.x | xx.x |
| Selenium | xx.x | xx.x | Selenium | xx.x | xx.x |
| Zinc | xx.x | xx.x | Zinc | xx.x | xx.x |
| Copper | xx.x | xx.x | Copper | xx.x | xx.x |
| Iron | xx.x | xx.x | Iron | xx.x | xx.x |

Test Group: Fortified malt based food + Dietary Counselling; Control Group: Dietary Counselling

Program: xxxxxx.sas

Source: Filename

Page x of y

Programming Note: The same structure will be in the next page for MONTH 9

Fortified malt based food

204477 Statistical Reporting and Analysis Plan Amendment 1 2 November 2018

Protocol: 204477

Program Run Date: DDDMMYYYY

Table 14.3.1.1
Treatment Emergent Adverse Event by System Organ Class and Preferred Term
Safety Population

Study Population: Safety Population (N=xxx)

| System Organ Class Preferred Term | Test Group (N = xxx) | | Control Group (N = xxx) | | Overall (N = xxx) | |
|---|-------------------------|-----|----------------------------|-----|----------------------|-----|
| | n (%) | nAE | n (%) | nAE | n (%) | nAE |
| NUMBER OF SUBJECTS WITH AT LEAST ONE AE | xx (xx.x) | xx | xx (xx.x) | xx | xx (xx.x) | xx |
| NUMBER OF SUBJECTS WITH NO AE | xx (xx.x) | | xx (xx.x) | | xx (xx.x) | |
| SOC 1 | xx (xx.x) | xx | xx (xx.x) | xx | xx (xx.x) | xx |
| PT 1 | xx (xx.x) | xx | xx (xx.x) | xx | xx (xx.x) | xx |
| PT 2 | xx (xx.x) | xx | xx (xx.x) | xx | xx (xx.x) | xx |
| --- | | | | | | |
| SOC 2 | xx (xx.x) | xx | xx (xx.x) | xx | xx (xx.x) | xx |
| PT 1 | xx (xx.x) | xx | xx (xx.x) | xx | xx (xx.x) | xx |
| PT 2 | xx (xx.x) | xx | xx (xx.x) | xx | xx (xx.x) | xx |
| --- | | | | | | |
| --- | | | | | | |

Fortified malt based food

204477 Statistical Reporting and Analysis Plan Amendment 1 2 November 2018

| System Organ Class Preferred Term | Test Group (N = xxx) | | Control Group (N = xxx) | | Overall (N = xxx) | |

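### The exploratory micronutrient and gut-marker correlations pool each arm's two schools, so a gap between the schools on both markers can create, mask or reverse a correlation

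*SAP*

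**What the plan says.** SAP 4.6 plans correlations between nine blood micronutrients (vitamins A, B12, D and E, folate, selenium, zinc, copper, iron) and two gut markers. For the levels, "gut integrity/health as measured by Lactulose: Mannitol test and Urinary Neopterin test will be computed at baseline and at visit 10". For changes from baseline, "gut integrity/health as measured by Lactulose: Mannitol test and Urinary Neopterin will be computed at month 9". It names no type of coefficient, no school stratum and no cluster term.

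The shell of Table 14.2.13.11 in SAP Attachment 1 is titled "Correlation between Blood Chemistry and Gut Integrity Health by Lactulose: Mannitol and Urinary Neopterin Test by Time Point". It is set on the mITT population and prints one column per gut marker under Test Group and again under Control Group. It has no school column, p-value, confidence interval or between-arm comparison. No shell is given for Table 14.2.13.12 (changes), so its layout by arm is an inference.

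SAP 3.3 gives the number of clusters: "This study is conducted in multiple (4) schools, with two schools in each product group". SAP 4.4.2 analyses the same micronutrients and gut markers by ANCOVA with school as a random effect and reports the intracluster correlation. The Amendment 1 rationale in SAP Section 5 is "Adjusting for the intracluster correlation is necessary for a valid analysis", but the change it supports covers the ANCOVA analyses only. By-school tables are planned for ill days alone (Tables 14.2.14.1 to 14.2.14.3).

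**The concern.** These coefficients are meant to describe how a child's micronutrient status relates to that child's gut integrity. A coefficient pooled over two schools also carries the difference between the two school means. If both markers differ between the schools, that difference enters the coefficient whatever the association among children.

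Such a gap is plausible, though the documents do not report one. Protocol 6.1 matches schools in pairs on size, socioeconomic profile and type, and Protocol 5.9 assigns the schools of a pair to test and control. With four schools, an arm's two schools come from different pairs and are not matched to each other. SAP Section 5 itself links socioeconomic status to dietary diversity and to children's immune status, so one school-level factor could move both kinds of marker. No planned summary table would reveal a school gap on the biomarkers.

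What is at stake is how an exploratory table is read.

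**Working it through.** **1. The plan's own figures.** The documents give no figure for the correlations, so the sample size is reproduced to obtain the cluster size and the only clustering strength that can be derived. SAP 1.4: "Mean of control was assumed to be 7.0 and standard deviation (SD) was 2.65, mean of test group was 6.3 and SD was 2.51", two-sided 5%, 80% power.
- Average variance = (2.65² + 2.51²)/2 = 6.661, so SD = 2.581. With a difference of 0.7, the t-test formula gives 214.4, rounded up to 215 per arm, as stated.
- 215 × 1.5 = 322.5, rounded up to 323 per arm, 646 in total.
- 323/0.7 = 461.4, rounded up to 462 per arm, 924 in total.

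All stated figures reproduce. With 323/2 = 161.5 evaluable children per school (equal sizes assumed), DE = 1 + (m − 1) × ICC gives ICC = 0.5/160.5 = 0.0031. That DE was set for ill days, not biomarkers.

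**2. Pooled correlation of two equal schools.** Let r_w be the within-school correlation and dx, dy the gaps between school means in within-school SDs. Pooling adds dx·dy/4 to the covariance and d²/4 to each variance:

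r_pooled = (r_w + dx·dy/4) / √[(1 + dx²/4)(1 + dy²/4)]

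| r_w | dx | dy | r_pooled |
|---|---|---|---|
| 0 | 0.08 | 0.08 | 0.002 |
| 0 | 0.2 | 0.2 | 0.01 |
| 0 | 0.5 | 0.5 | 0.0625/1.0625 = 0.06 |
| 0 | 0.8 | 0.8 | 0.14 |
| 0 | 1.0 | 1.0 | 0.25/1.25 = 0.20 |
| 0 | 0.5 | 0 | 0 |
| 0.20 | 0.5 | −0.5 | 0.1375/1.0625 = 0.13 |
| 0.20 | 1.0 | −1.0 | −0.05/1.25 = −0.04 |

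The gap can therefore create, mask or reverse a correlation. A gap on one marker only adds nothing and merely dilutes a real association.

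**3. How large a gap goes with a given ICC.** The SD of the difference between two school means is √[2·ICC/(1 − ICC)] within-school SDs: 0.08 at ICC 0.0031, 0.32 at 0.05, 0.47 at 0.10 and 0.71 at 0.20.

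**4. Simulation.** 10,000 trials, 161 children in each of two schools, no association within schools, independent school effects on the two markers. As a yardstick only, since no test is planned: |r| above 0.109 corresponds to two-sided p < 0.05 at n = 322. The ICCs are assumptions.

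| ICC | Pooled, share beyond 0.109 | School-centred, share nominally significant |
|---|---|---|
| 0.003 | 5.0% | 5.0% |
| 0.01 | 5.4% | 5.2% |
| 0.05 | 7.6% | 5.4% |
| 0.10 | 13.2% | 4.9% |
| 0.20 | 27.5% | 5.3% |

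Centring each marker on its school mean holds the nominal rate at every ICC tried. The spread of the coefficient after centring (SD 0.055 to 0.056) equals that of an unclustered sample, so nothing visible is lost.

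**The case against.** The strongest reply is that these are descriptive coefficients. They are exploratory, and the shell has no p-value, interval or threshold, so an error rate describes a test that nobody planned. This stands, and the rates above serve only as a yardstick. It does not remove the bias in the coefficient itself, which step 2 shows without any test.

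A second reply is that the artefact needs a gap on both markers, and that at the only ICC the documents imply it vanishes. Both parts are correct. The implied ICC belongs to ill days, however, and does not settle the question for serum and urine markers.

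A reader might infer that a school gap would show up as a test-versus-control difference and be taken for a product effect. The documents do not support stating this: no comparison of coefficients between arms is planned, and pair matching could mirror a socioeconomic gap in both arms. In 4,000 simulated trials with school effects fully shared within pairs, a contrast between arms would pass p < 0.05 in 4.9%, 5.3% and 4.6% at ICC 0.05, 0.10 and 0.20. With effects half shared it would pass in 7.0%, 11.3% and 25.8%. An apparent arm difference thus depends on school differences that the matching missed, and on the reader making the comparison.

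A reader might also see a contradiction of Amendment 1. Its sentence justifies a change to the ANCOVA analyses, so the correlations are left uncovered rather than in conflict with it. Differences in sampling dates between schools are not documented and are not relied on here.

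**Conclusion.** The point holds as a conditional one. The plan pools two unmatched schools per arm with no allowance for school, while its ANCOVAs of the same biomarkers do allow for it. If an arm's two schools differ on both markers, the coefficient is distorted: 0.01 at gaps of 0.2 SD, 0.06 at 0.5 SD and 0.20 at 1 SD when there is no child-level association. Whether this happens rests on biomarker ICCs that have to be assumed: negligible near 0.003, material from about 0.05 to 0.10 upward. The figures assume two schools of equal size in each arm.

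The point is strongest for Table 14.2.13.11. In Table 14.2.13.12, change scores remove stable differences between schools, so only differing changes could act there. It would be too strong to say that the tables will show false correlations or a false product effect. This is a free improvement to an exploratory display, with no bearing on the primary or secondary analyses or the sample size.

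**What to change.** In SAP 4.6 and Tables 14.2.13.11 and 14.2.13.12, state the type of coefficient and compute it with school partialled out, for example by centring both variables on their school mean within each arm. Add a footnote that the values are within-school and descriptive. The layout by arm, including at baseline, may stay; pooling the arms at baseline is a matter of preference.

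The cost is 1 degree of freedom per arm out of about 320, a small programming change and a footnote. If the school gaps prove trivial, the coefficients will hardly move.
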